- h. The MMTT will be a 4-hour assessment to be conducted in the morning after an overnight fast. All other blood samples should be drawn prior to the MMTT. When MMTT occurs on study agent dosing days, study agent should be administered after the MMTT.
- i. Type 1 diabetes autoantibodies including glutamic acid decarboxylase (GAD-65), insulin, IA-2, ZnT8 and ICA.
- j. Females of childbearing potential must have a negative serum pregnancy at screening and a negative urine pregnancy test prior to administration of study agent.
- k. Specifics tests are described in Section 9.6. Note: Fasting lipid panel only done at screening, Week 12, 26, 38, 52, 78 and 104. Coagulation panel (PT/PTT/INR) only done at screening.
- l. Viral serology panels to include: CMV, EBV, HepB, HepC, HIV.
- m. Quantitative PCR testing for CMV and EBV.
- n. The same serum samples may be used for the measurement of golimumab concentration, detection of antibodies to golimumab and amounts of free/total TNF α . Drawing of these samples must take place prior to study agent administration at visits where study agent dosing occurs. Priority of analysis depending on sample volume is: PK, ADA, NAB, total TNF, free TNF. Additional serum samples for golimumab concentration and Total/Free TNF α will be collected at Week 33 and Week 45.
- o. **Required** pharmacogenomic assessment of molecular MHC haplotype.
- p. Anticipated assessments may include T- and B-cell subset analysis by multicolor flow cytometry and serum protein/cytokine profiling.
- q. Optional pharmacogenomics assessments anticipated to include insulin DNA methylation.
- r. End of Study Visit assessments: May be used in instances where subjects withdraw early from the study, see Section 10.2.
- s. All biomarker and pharmacogenomics samples must be collected prior to study agent administration.

Open-Label Extension Period

Open-Label Extension Period											
Study Designation	Screening^q	Active Treatment^{b,c}									Post-Treatment^d
Study Week^a		OL 0	OL 2	OL 4	OL 12	OL 20	OL 28	OL 36	OL 44	OL 52 (EOSV) ⁿ	OL 60 or 10 weeks post last dose
Study Day^a (visit window in days)	-14 to -1	1	15 (±1)	29 (±3)	85 (±3)	141 (±3)	197 (±3)	253 (±3)	309 (±3)	365 (±3)	421 (±7)
Study Procedure											
Screening/Administrative											
Informed consent/assent (ICF)	X ^p										
Inclusion/exclusion criteria evaluation/review	X	X									
Dispense dosing, insulin and hypoglycemia paper diary ^c	X	X	X	X	X	X	X	X	X		
Clinical Assessments / Ongoing Review											
Full Physical examination	X									X	X
Brief physical examination		X	X	X	X	X	X	X	X		
Vital signs	X	X	X	X	X	X	X	X	X	X	X
Height & Body weight measurement		X			X		X		X		X
Interval history and paper diary review		X	X	X	X	X	X	X	X	X	
Previous/concomitant medication review	X	X	X	X	X	X	X	X	X	X	X
IDAA1c	X	X	X	X	X	X	X	X	X	X	
Adverse events	X	X	X	X	X	X	X	X	X	X	X
Tuberculosis (TB) exposure review	X	X	X	X	X	X	X	X	X	X	X
Randomization and Study Agent Administration											
Dose determination and modification		X			X		X		X		
Required study agent administration at study site ^f		X	X	X	X	X	X	X	X		
Subjects participating in self-administration^b											
Injection training by site personnel ^b		X									

Open-Label Extension Period											
Study Designation	Screening ^q	Active Treatment ^{b,c}									Post-Treatment ^d
Study Week ^a		OL 0	OL 2	OL 4	OL 12	OL 20	OL 28	OL 36	OL 44	OL 52 (EOSV) ⁿ	OL 60 or 10 weeks post last dose
Study Day ^a (visit window in days)	-14 to -1	1	15 (±1)	29 (±3)	85 (±3)	141 (±3)	197 (±3)	253 (±3)	309 (±3)	365 (±3)	421 (±7)
Study Procedure											
Distribute study agent injection devices				X	X	X	X	X	X		
Return study agent injection devices					X	X	X	X	X	X	
Subject Reported Data / Paper Review											
Insulin use report review	X	X	X	X	X	X	X	X	X	X	
Hypoglycemia event review		X	X	X	X	X	X	X	X	X	X
Study agent self-administration review ^b				X	X	X	X	X	X	X	
Clinical Laboratory Assessments											
4h - Mixed-meal tolerance test (MMTT) ^g	X						X			X	
HbA1c	X	X	X	X	X	X	X	X	X	X	X
QuantiFERON-Gold test	X										
Serum pregnancy test ^h	X										
Urine pregnancy test ^h		X	X	X	X	X	X	X	X	X	X
Hematology ⁱ	X	X	X	X	X	X	X	X	X	X	X
Chemistry ⁱ	X	X	X	X	X	X	X	X	X	X	X
Viral serology ^j	X										
Polymerase chain reaction (PCR) Viral load ^k	X				X			X		X	
Clinical Pharmacology											
Golimumab concentration ^l		X	X	X	X	X	X	X	X	X	
Antibodies to golimumab ^l		X	X	X	X	X	X	X	X	X	X
Free/total TNF α ^l		X	X	X	X	X	X	X	X	X	X
Biomarkers and Pharmacogenomics^o											
Peripheral blood mononuclear cell (PBMC) sample collection ^m	X									X	
Serum biomarker sample ^m		X								X	

Abbreviations: EOSV=End of Study Visit, ICF=informed consent, IDAA1c=insulin dose-adjusted HbA1c, MHC=major histocompatibility complex, MMTT=mixed-meal tolerance test, OL=open-label, PBMC=peripheral blood mononuclear cell, PCR=polymerase chain reaction, TB=tuberculosis, TNF α =tumor necrosis factor alpha

- a. The study visit Week and target study visit Day are indicated and calculated based on the day of first dose. Acceptable windows for study visits in days before (-) or after (+) target study visit day are indicated and based on if study agent dosing will be given at that visit and time enrolled in the study.
- b. Subjects/caregivers will be given the option for at home “self-administration” for study agent doses after OL Week 4, since the dosing schedule for subject is q2w through OL Week 50. Training on self-administration will be provided at OL Week 0 (See Section 6.2 for details). These subjects will record data regarding self-administration in the paper diary (See Section 7.1.1.1) or if self-administering at the site, the data will be recorded in the study site’s documents, not in the paper diary.
- c. Subjects not participating in self-administration will schedule study agent dosing-only visits every 2 weeks through OL Week 50 (see Section 9.1.39.1.5).
- d. The post-treatment visit will be conducted for all subjects at OL Week 60 or 10 weeks after the last dose of study agent to collect SAEs and AEs of interest since the last visit unless the subject has died, has been lost to follow-up, or has withdrawn consent.
- e. For those who do not meet study criteria or choose not to participate in this study, instructions on how to return the paper diary will be given.
- f. This does not represent all study agent dosings. At OL Weeks 0, 2, and 4, administration will occur during study visits. At OL Weeks 12, 20, 28, 36, 44, and 50 study visits where study agent will be administered, either subjects/caregivers or study staff may administer the injection. At the required visits in this table, drawing of pharmacokinetic/immunogenicity (ie, golimumab concentration and antibodies to golimumab) samples must take place **prior** to study agent administration at visits where study agent dosing occurs. Following study agent administration subjects will be observed for 30 minutes for symptoms of injection reactions. The last dose of study agent is to be administered at Week 50. See Section 6.1 and Section 9.1.5.3.
- g. The MMTT will be a 4-hour assessment to be conducted in the morning after an overnight fast. All other blood samples should be drawn prior to the MMTT. When MMTT occurs on study agent dosing days, study agent should be administered after the MMTT.
- h. Females of childbearing potential must have a negative serum pregnancy at screening and a negative urine pregnancy test prior to administration of study agent.
- i. Specifics tests are described in Section 9.6.1. Note: Lipids will not be measured during the open-label extension period. Coagulation panel (PT/PTT/INR) only done at screening.
- j. Viral serology panels to include: CMV, EBV, HepB, HepC, HIV.
- k. Quantitative PCR testing for CMV and EBV. For the open-label extension period, subjects may begin open-label study agent while EBV PCR results are pending and if he/she meets all other inclusion/exclusion criteria. If EBV PCR results come back positive, subject must immediately stop treatment and be withdrawn from the study.
- l. The same serum samples may be used for the measurement of golimumab concentration, detection of antibodies to golimumab and amounts of free/total TNF α . Drawing of these samples must take place prior to study agent administration at visits where study agent dosing occurs. Priority of analysis depending on sample volume is: PK, ADA, NAB, total TNF, free TNF.
- m. Anticipated assessments may include T- and B-cell subset analysis by multicolor flow cytometry and serum protein/cytokine profiling.
- n. End of Study Visit assessments: May be used in instances where subjects withdraw early from the study, see Section 10.2. Subjects who permanently discontinue active treatment during the open-label extension period will have their end-of-study visit followed by the post-treatment visit 10 weeks later.
- o. All biomarker and pharmacogenomics samples must be collected prior to study agent administration.
- p. The retreatment screening visit should occur within 4 weeks of site notification of responders.
- q. The optional screening visit should take place no later than 21 days after the subject has been offered the opportunity to enter open-label extension period and in any event must occur within 14 days prior to Week 104.

ABBREVIATIONS

ADA	American Diabetes Association
ADR	adverse drug reaction
AE	adverse event
ALT	alanine aminotransferase
ANCOVA	analysis of covariance
anti-HBc	hepatitis B core antibody
ARC	Anticipated Event Review Committee
AS	ankylosing spondylitis
AST	aspartate aminotransferase
AUC	area under the concentration-time curve
BCG	Bacille Calmette-Guérin
BG	blood glucose
BSA	body surface area
C responders	C-peptide responders
CD	Crohn's Disease
CDC	Centers for Disease Control and Prevention
CDE	certified diabetes educator
CL/F	apparent total systemic clearance
CMV	Cytomegalovirus
CRF	case report form(s) (paper or electronic as appropriate for this study)
C+R responders	C-peptide and remission score responders
DBL	data base lock
DKA	diabetic ketoacidosis
DMC	Data Monitoring Committee
EBV	Epstein-Barr virus
eDC	electronic data capture
eDiary	electronic diary
FDA	Food and Drug Administration
GAD-65	Glutamic acid decarboxylase
GCP	Good Clinical Practice
HbA1c	hemoglobin A1c
HBsAg	hepatitis B surface antigen
HBV	hepatitis B virus
HCV	hepatitis C virus
HIV	human immunodeficiency virus
HPV	human papillomavirus
IAC	Interim Analysis Committee
IDAA1c	insulin dose-adjusted HbA1c
IB	Investigator Brochure
ICF	informed consent form
ICH	International Conference on Harmonisation
IEC	Independent Ethics Committee
IFU	instructions for use
IL	interleukin-
IND	Investigational New Drug
IRB	Institutional Review Board
IWRS	interactive web response system
LQC	lowest quantifiable concentration
MedDRA	Medical Dictionary for Regulatory Activities
MHC	major histocompatibility complex
mITT	modified intent-to-treat
MMRM	mixed model for repeated measures
MMTT	Mixed-meal Tolerance Test
MS	multiple sclerosis
MTX	methotrexate

NAb	neutralizing antibody
NONMEM	NONlinear Mixed Effects Modeling
NPH	Neutral Protamine Hagedorn
OL	open-label
PBMC	peripheral blood mononuclear cell
PCR	polymerase chain reaction
PD	pharmacodynamic(s)
PE	physical examination
PFS-U	UltraSafe Passive [®] Delivery System assembled with PFS
pJIA	polyarticular juvenile idiopathic arthritis
PK	pharmacokinetic(s)
PQC	Product Quality Complaint
PsA	psoriatic arthritis
PsO	psoriasis
q2w	every 2 weeks
q4w	every 4 weeks
R responders	remission score responders
RA	rheumatoid arthritis
SAE	serious adverse event
SAP	Statistical Analysis Plan
SC	subcutaneous
SD	standard deviation
SIPPM	Study Site Investigational Product and Procedures Manual
SLE	systemic lupus erythematosus
SUSAR	suspected unexpected serious adverse reaction
T1D	type 1 diabetes
TB	tuberculosis
TE	target engagement
TNF α	tumor necrosis factor alpha
UC	ulcerative colitis
ULN	upper limit of normal
V/F	apparent volume of distribution

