Following database lock for the double-blind treatment period (Week 52), subjects who are still in the off-therapy follow-up period (Week 52 to 104 visits), who were on active drug during the double-blind period and who meet the response criteria will be offered the option to participate in the open-label extension period if eligibility criteria are met. Prior to initiating open-label screening assessments, subjects and parents/legal guardians will sign updated informed consent form/assent forms.

Subjects who did not meet the response criteria at Week 52 will continue the off-therapy follow-up period.

Subjects who met the response criteria but either declined to participate in the open-label extension period, or were determined to be on placebo, will continue the off-therapy follow-up period as planned.

SUBJECT POPULATION

Male or female subjects 6 through 21 years of age who meet the American Diabetes Association (ADA) standard T1D criteria within 100 days of randomization. Subjects must be positive for at least 1 of the following diabetes-related autoantibodies obtained at study screening:

- Glutamic acid decarboxylase (GAD-65)
- IA-2
- ZnT8
- ICA; or
- Insulin (if obtained within 10 days of the onset of exogenous insulin therapy)

Subjects must be medically stable on the basis of physical examination, medical history, and vital signs performed at screening and have a stimulated C-peptide level ≥ 0.2 pmol/mL following a 4-hour MMTT obtained at study screening.

The responders for open-label extension period must meet the MMTT criteria at Screening for the open-label extension period. If the most recent MMTT is < 3 months ago, a repeat MMTT is not required. Subjects who had their most recent safety laboratory samples drawn within 1 month prior to screening do not need a repeat; eligibility will be assessed based on these most recent laboratory tests. For C-responders who are lacking the necessary information to calculate IDAA1c score, an HbA1c will be performed and 10 days of insulin dose information will be required.

DOSAGE AND ADMINISTRATION

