9. STUDY EVALUATIONS

9.1. Study Procedures

9.1.1. Overview

- The [Time and Events Schedule](#) summarizes the frequency and timing of efficacy, PK, immunogenicity, Pharmacodynamics, biomarker, pharmacogenomic, and safety assessments applicable to this study.
- During the double-blind period, a 4-hour MMTT will be performed during screening, and at Weeks 12, 26, 38, 52, 78, and 104¹². During the open-label extension period, a 4-hour MMTT will be performed to establish eligibility criteria unless the previous MMTT was <3 months ago and will also be performed at OL Screening and OL Weeks 28 and 52. For C-responders who are lacking the necessary information to calculate IDAA1c score, an HbA1c will be performed and 10 days of insulin dose information will be required. This test is to be performed in the morning after an overnight fast. Subjects are to follow the dietary and insulin use guidelines as described in [Attachment 3](#) to perform the MMTT.
- Subjects/caregivers will collect data related to diabetes management, hypoglycemic events, and study agent dosing using sponsor-supplied eDiary and glucometer (for the double-blind period) and paper diary (for the open-label extension period).
- PK and Immunogenicity samples must be collected before study agent administration.
- Additional serum or urine pregnancy tests may be performed, as determined necessary by the investigator or required by local regulation, to establish the absence of pregnancy at any time during the subject's participation in the study.
- Blood collection:
 - The total blood volume to be collected from each subject, including during screening, the 52-week treatment period and 52-week off-therapy follow-up period is approximately 436 mL for subjects <35 kg and 505 mL in subjects ≥35 kg. During the open-label extension period, approximately 210 mL for subjects <35 kg and 234 mL for subjects ≥35 kg will be drawn.
 - It is recognized that the amount of blood that may be drawn for research purposes in adults and children may not exceed certain limits, both at a single visit and over a set amount of time. Guidance for blood drawing in this study is:

Adult Subjects (18 years of age and older)

The amount of blood that may be drawn for research purposes shall not exceed 10.5 mL/kg or 550 mL, whichever is smaller, over any 8-week period.

Pediatric Subjects (6 Through 17 Years of Age):

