The last dose of study agent is to be administered at the Week 52 study visit. Subjects will remain in the study until Week 104, continue recording data in their eDiary and followed for evaluations of safety, PK/anti-drug antibodies, and durability of response. Subjects will have assessments only at Week 78 and Week 104. All safety and efficacy assessments will be performed at these visits according to the [Time and Events Schedule](#). The visit windows for these 2 visits are \pm 10 days of the target visit day.

During the treatment and off-therapy follow-up periods subjects will continue to receive intensive management of their diabetes and maintain tight glycemic control according to the current ADA.⁶⁷

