9.1.5. Open-Label Extension Period

Subjects meeting the inclusion criteria applicable for responders and who are willing to participate will restart active study treatment in the open-label extension period.

9.1.5.1. Active Treatment Period: OL Weeks 0 To 52

Restart: OL Week 0

Restart will occur no later than 14 days after screening is initiated and will be designated as Week 0 and Day 1 of the study. In no event can a subject be restarted if they have completed the Week 104 visit. At this visit, inclusion and exclusion criteria, concomitant medications, and laboratory evaluations should be reviewed and documented to determine that a subject remains

eligible for participation in the study. All paper diary data collected since screening will be reviewed by clinic staff. Subjects should have at least 10 days of daily insulin use immediately preceding restart. Subjects will be restarted to receive golimumab as described in Section 3.1. Subject weight and height will be obtained to determine dose and device.

The dose of study agent (golimumab) will be administered at the study site. Subjects should be monitored for at least 30 minutes following injection and be observed for any adverse reactions, including injection site reactions (See Section 9.9). Subjects/caregivers who want to participate in study agent “self-administration” outside of some study visits begin training on using the sponsor-supplied single-use injection devices (See details Section 6.2). Additional training on the paper diary and glucometer will be given as needed.

Future target dosing and study visit days will be calculated based on the day of initial dosing (Week 0) and will not be redefined later during the study. Therefore, the study staff are encouraged to discuss the study visit days with subjects/caregivers and consider this schedule to determine what might be the anticipated (ie, day of the week) for future dosing and study visits. Specific study visits and study agent treatment windows and impact on study compliance is detailed in Section 7.

At this visit, subjects/caregivers will be supplied with a calendar with target dosing days and target study visit days that show dosing and visit windows (See Section 7.1.2.1).

Study Visits: OL Weeks 2 and 4

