9.2.1.1. Efficacy Evaluations - Open-Label Extension Period

- A 4-hour MMTT will be performed to assess C-peptide levels and the C-peptide AUC at OL screening (unless performed <3 months ago), OL Week 28, and OL Week 52. For C-responders who are lacking the necessary information to calculate IDAA1c score, an HbA1c will be performed and 10 days of insulin dose information will be required. For additional details, see the [Time and Events Schedule](#).
- During the open-label extension period, subjects may use either fingersticks or continuous glucose monitoring (CGM) at the discretion of the investigator and/or according to local practice. The subjects will not be required to download BG values from the eDiary.
- Hemoglobin A1c (as % HbA1c) and insulin as U/kg body weight/day. An HbA1c measurement will be done at each study visit and subjects should record the type and amount of insulin they have used during the 10-day period.
- Hypoglycemic events, defined as a BG level of ≤ 70 mg/dL or clinical sequelae consistent with hypoglycemia without a BG reading, will be documented throughout the study.
- Records of glucose measurements, insulin use and hypoglycemic events and communication with the subject will be kept in source documentation, on the appropriate CRF, or in the patient diary.

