9.2.2.3. Other Endpoints

- Change from baseline in MMTT-stimulated 4-hour C-peptide AUC over time.
- Change from baseline in comparative MMTT-stimulated 2-hour C-peptide AUC over time.
- Change from baseline in MMTT-stimulated C-peptide over time.
- Change from baseline in insulin use in units per kilogram body weight per day over time.
- The proportions of subjects with hypoglycemia from baseline to Week 104, from baseline to Week 52 and from Week 52 to Week 104.

- The event rates of hypoglycemia from baseline to Week 104 and from Week 52 through Week 104.
- Change from baseline in HbA1c levels over time.
- Proportion of subjects with peak MMTT-stimulated C-peptide ≥ 0.2 pmol/mL over time.
- Time to peak MMTT-stimulated C-peptide < 0.2 pmol/mL.

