10.2. Discontinuation of Study Treatment/Withdrawal from the Study

Discontinuation of Study Treatment

A subject will **not** be automatically withdrawn from the study if they have to temporarily or permanently discontinue treatment before the end of the treatment regimen.

If a subject permanently discontinues study treatment for any reason before the end of the treatment phase (Week 52), they should be encouraged to continue with all scheduled visits to and including the final study visit (Week 104), but without receiving study agent administration. If unwilling or unable to participate in all visits, subjects should be encouraged to participate in as many of the planned study visits as possible for continued assessment, but without receiving study agent administration. If the subject is not able to participate in the next 2 sequential study visits that include an MMTT, they should be encouraged to return for the End of Study visits (per the [Time and Events](#) Tables) approximately 10 weeks after their last dose administration.

Similarly, if a subject withdraws following the treatment period (after Week 52) they should be encouraged to participate in the Week 78 and Week 104 visits, as applicable. If the subject is unwilling or unable to complete any of the remaining scheduled study visits, they should be encouraged to return for the End of Study visit (per [Time and Events Schedule](#)) approximately 10 weeks after their last dose administration, as applicable.

Following randomization (ie, between Week 0 and Week 104), consecutive MMTTs should not be repeated if the time interval between them is less than 10 weeks. The MMTT can be repeated in less than 10 weeks only for repeat testing during the screening period or for rescreening.

SAEs will be requested to be submitted for subjects who withdraw early from the study for a year after their last study agent dose (Section [12.4.1](#)).

Subjects who permanently discontinue active treatment during the open-label extension period will have their end-of-study visit followed by the post-treatment visit 10 weeks later.

Study treatment may be temporarily or permanently discontinued due to events described below.

- Events That Result in Permanent Discontinuation of Study Treatment.
 - The investigator believes that for safety reasons or tolerability reasons it is in the best interest of the subject to discontinue study treatment.
 - The subject becomes pregnant.

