11. STATISTICAL METHODS

Statistical analysis will be done by the sponsor or under the authority of the sponsor. A general description of the statistical methods to be used to analyze the efficacy and safety data is outlined below. Specific details will be provided in the Statistical Analysis Plan (SAP).

Descriptive statistics (eg, mean, median, standard deviation [SD], minimum, and maximum) will be used to summarize continuous variables. Counts and percentages will be used to summarize categorical variables. Graphic data displays may also be used to summarize the data.

Efficacy analyses will be based on the modified intent-to-treat (mITT) population (ie, all randomized subjects who have received at least 1 dose of study agent). Subjects included in the efficacy analyses will be summarized according to their assigned treatment group regardless of whether or not they receive the assigned treatment.

Safety analyses will include all subjects who received at least 1 dose of study treatment.

Pharmacokinetics and immunogenicity analyses for golimumab will include all subjects who receive at least 1 dose of golimumab and have at least 1 post-dose sample collection.

The baseline measurement is defined as the closest measurement taken at or before the time of the Week 0 administration for the double-blind period. The baseline measurement for the open-label extension period is the closest measurement taken at or before the time of the Week 0 administration of the open-label extension period.

No hypotheses testing will be performed for open-label extension period, and data generated will be summarized descriptively.

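### A waived open-label screening meal test lets the open-label C-peptide baseline predate restart by up to about 105 days, so change from that baseline can include time before re-treatment (minor; exploratory results only)

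*Protocol*

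**What the plan says.** **The waiver.** The Synopsis (Subject Population) states "If the most recent MMTT is < 3 months ago, a repeat MMTT is not required". The same exemption stands in the Synopsis (Efficacy Evaluations) and in Sections 3.1 and 4.1.2. Section 9.2.1.1 schedules the OL meal tests at "OL screening (unless performed <3 months ago), OL Week 28, and OL Week 52".

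**The baseline.** Section 11 says "The baseline measurement for the open-label extension period is the closest measurement taken at or before the time of the Week 0 administration" of that period. It sets no maximum age. The OL Time and Events Schedule has no MMTT at OL Week 0. It does have HbA1c and a review of insulin use there.

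**The timing.** Section 9.1.5.1: "Restart will occur no later than 14 days after screening is initiated". Section 9.1.3.3: "The last dose of study agent is to be administered at the Week 52 study visit". No study agent is scheduled between that visit and OL Week 0.

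**The endpoints.** Section 9.2.2.3 lists "Change from baseline in MMTT-stimulated 4-hour C-peptide AUC over time". Sections 9.2.2.4 and 11.3.1 carry all double-blind efficacy endpoints into the extension as exploratory and descriptive. They add a within-subject comparison of progression between the two periods, to be made if judged reasonable. The SAP is limited to the Week 52 lock (SAP Section 1) and contains no OL analysis.

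**Conflicting wording.** Section 9.1.1 first applies the waiver and then says the test "will also be performed at OL Screening and OL Weeks 28 and 52". The OL schedule marks an MMTT at screening, and its footnote g gives no waiver. Section 9.1.2.1 includes the MMTT in OL screening. Section 10.2, which governs Week 0 to Week 104, says "consecutive MMTTs should not be repeated if the time interval between them is less than 10 weeks".

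**The concern.** For a subject whose screening MMTT is waived, the C-peptide baseline is the earlier follow-up test. The change from OL baseline then runs from that test, not from the restart of golimumab, and nothing in the documents adjusts for the gap. The gap differs between subjects. It also differs between endpoints within a subject, because HbA1c and insulin use are measured at OL Week 0.

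If C-peptide falls while treatment is stopped, part of that fall is reported as change during the extension. That makes re-treatment look worse and distorts the comparison of progression between the two periods. The extension describes re-treatment in a small, uncontrolled group, so the start point of its main metabolic measure deserves care.

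**Working it through.** **1. The plan's own figure.** The planning means are 0.385 (placebo) and 0.635 (golimumab), with SD 0.215 on log(AUC+1), 54 and 27 subjects and two-sided alpha 0.05 (Protocol 11.2, SAP 1.4). The difference is ln(1.635) − ln(1.385) = 0.1659. Power from the noncentral t with 79 df is 89.9%, against the stated 90%. The planning means are therefore being read on the intended scale. The point itself does not depend on power.

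**2. Maximum age of the OL baseline.** Take three months as 91 days, measured at OL screening, and add up to 14 days to restart: 91 + 14 = 105 days (15 weeks). With a fresh screening test the maximum is 14 days.

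**3. Share of the change interval before re-treatment,** gap / (gap + days from OL Week 0 to the visit):

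| Gap | OL Week 28 (196 days) | OL Week 52 (364 days) |
|---|---|---|
| 105 days | 105/301 = 35% | 105/469 = 22% |
| 91 days (three months counted to restart) | 91/287 = 32% | 91/455 = 20% |
| 14 days (fresh test) | 14/210 = 6.7% | 14/378 = 3.7% |

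This step needs no assumption about decline.

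**4. How often the waiver could apply.** Follow-up tests fall at Weeks 52 and 78, so a test is under 13 weeks old in Weeks 52–65 and 78–91. Offers come after the Week 52 database lock, which waits for all subjects to complete Week 52 (Sections 3.1, 3.2.1). Assume subjects are evenly spread over follow-up and OL screening lags the last Week 52 visit by d weeks. Eligible subjects then lie in Weeks 52+d to 104.
- d = 4: (9 + 13)/48 = 46%
- d = 8: (5 + 13)/44 = 41%
- d = 13: 13/39 = 33%

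A Week 52 test serves as baseline for 5/44 = 11% at d = 8 and for none at d = 13.

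**5. Illustrative size.** The documents give no off-therapy decline rate. Assume a baseline AUC of 0.66 pmol/mL (Section 3.2.1 expects the median near this) and linear decline on log(AUC+1). The placebo rate is (ln 1.66 − ln 1.385)/52 = 0.00348 per week. Over 15 weeks the drop u is that rate × 15 × the assumed fraction, and the AUC fall is 1.66 × (1 − e^(−u)).
- 25%: u = 0.013, AUC falls 0.0215/0.66 = 3%
- 50%: u = 0.026, AUC falls 0.0428/0.66 = 6%
- 100%: u = 0.052, AUC falls 0.0845/0.66 = 13%
- 0%: no effect

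At the full placebo rate, moving the assumed baseline to 0.56 gives u = 15 × 0.00229 = 0.034 and a fall of 9%. Moving it to 0.76 gives u = 15 × 0.00461 = 0.069 and a fall of 15%. For scale, the responder definition treats a fall of up to 5% as stable.

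**The case against.** **Low stakes.** OL efficacy is exploratory, descriptive and untested. The period comparison is optional, has no stated method, and need not use the OL baseline. Section 9.7 requires actual sampling dates, so a date-based analysis is already possible. The double-blind period has a milder version of the same feature: its MMTT is up to 28 days before Week 0, while HbA1c is repeated at Week 0. All of this stands, and it is why the point is minor.

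**The gap is not all drug-free.** A reader might take the whole gap as untreated time. For a Week 52 baseline that is wrong. Footnote h of the double-blind schedule puts dosing after the MMTT, and the last dose is given at that visit, so one dose follows the test. Section 3.2.2 says steady state takes at least three months with routine dosing, which suggests slow elimination. The objection does not reach a Week 78 baseline in the same way.

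**Frequency.** A reader might count 26 of 52 follow-up weeks and infer that half of restarts are affected. That ignores the wait for the Week 52 lock; 33% to 46% is the better range. Footnote q of the OL schedule and Sections 9.1.2.1 and 9.1.4 also place OL screening within the 14 days before Week 104. Read literally, the Week 78 test would then be at least 158 days old (day 715 − day 557) and the waiver could never apply. That reading sits badly with the 21-day rule in the same sentence, so the passages leave the frequency open.

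**Size.** A reader might subtract the planning means from 0.66, obtain yearly losses of 0.275 (placebo) and 0.025 (golimumab), and infer that 13 untreated weeks turn an apparent loss of 0.025 into 0.025 + 0.069 = 0.094, nearly fourfold. The documents do not support this. The 0.66 is a stratification cut-off expected near the median, not a baseline mean. The full placebo rate is applied to subjects selected for stable C-peptide or remission. The denominator is also tiny: with a baseline of 0.56 the planned golimumab mean would be a rise.

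**Conclusion.** The mechanism holds on the text. The waiver, a baseline rule with no age limit and the absence of an MMTT at OL Week 0 together allow a C-peptide baseline about 105 days old at restart. Up to 35% of the OL Week 28 interval and 22% of the OL Week 52 interval can precede re-treatment, varying by subject and unadjusted.

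Whether this biases results depends on off-therapy decline in responders, which the documents do not give. Under the stated assumptions the AUC shift at the maximum gap is about 3% to 13%; it could be near zero. If there is decline, the error runs against golimumab. The share of restarts affected, 33% to 46%, assumes even spread and lags of 13 to 4 weeks.

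A reader might infer that the trial's main efficacy result is at risk. It is not: the Week 52 primary analysis uses neither the OL baseline nor the OL tests. This is a minor point, worth acting on because the remedy is nearly free.

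**What to change.** In Section 11.3.1 and the analysis plan for the extension:

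1. Tabulate, by subject and in summary, the interval from the OL-baseline MMTT to OL Week 0.
2. Present OL C-peptide by actual day relative to OL Week 0. Show change from OL baseline separately for subjects with an MMTT in the −14 to −1 day screening window. For all subjects, add the change from OL Week 28 to OL Week 52, which lies wholly within the treatment period and does not depend on baseline age.
3. Reconcile Section 9.1.1, the OL schedule with its footnote g, and Section 9.1.2.1 with the waiver. Reconcile the OL screening timing in footnote q and Sections 9.1.2.1 and 9.1.4 as well. The 10-week spacing rule in Section 10.2 belongs in that reconciliation, because testing everyone at OL screening would conflict with it for recently tested subjects.

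A model with a change of slope at OL Week 0 is optional only. A subject waived on the Week 52 test has no later MMTT before restart, so that subject's off-drug slope would have to be borrowed from others.

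The cost is analysis wording and a few descriptive displays, with no added visit, blood draw or meal test. The drawback is that the separate groups will be small.
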